6 DESIGN OF THIS CLINICAL STUDY

6.1 *Description*

This is a prospective, randomized, double-blind, sham controlled multi-center clinical trial “Migraine Treatment with Nerivio Migra electro stimulation device”. The study will enroll up to 248 patients diagnosed with migraine with and without aura, per the inclusion and exclusion criteria. These patients will be individually and randomly assigned to either treatment group or control group. For sham control, short electrical pulses of amplitude range similar to that of the treatment programs will be administered at very low frequency (0.1-0.5 Hz). The rationale underlying selection of sham control settings is that, on the one hand, pulses are perceivable and the user is able to manipulate their intensity similarly to the case of treatment programs, while, on the other hand, no clinically relevant treatment is delivered, based on existing knowledge of parameters range of electro stimulation treatments [5-7, 18].

Following successful screening, enrollment interview and signing of informed consent, participants will be provided with an active Nerivio Migra or identically looking sham device and trained to perform treatment and provide feedback via the smartphone application. Ratio between treatment and control groups will be 1:1.

Baseline information including mean frequency and severity of migraine attacks, occurrence of other headaches, presence of ICHD-3 diagnostic criteria for migraine with and without aura and use of preventive and rescue medications will be recorded.

Investigational devices will be programmed in active or sham mode with a 1:1 ratio, in order to achieve the desired ratio between active and control groups sizes, stratified with by use of preventive medications.

Study flow is schematically presented in the figure below.

[figure not shown]

Figure 4. Study Design

Following enrollment, the study will be conducted in three stages.

Stage One. In stage one (roll-in phase) recruited participants will be reporting their migraine attacks per ICHD-3 diagnostic criteria, including presence of aura, using an electronic migraine diary installed on their smartphones. Duration of this phase is one month.

Stage Two. This will be the parallel arm treatment stage.

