7.4 Sample Size Estimation

The sample size for this study was calculated to test the above described null hypothesis with a chi-squared test, even though the final analysis may employ a regression model.

In the pilot study, the percentage of responders in the relevant treatment arm was 30%, while the percentage of responders in the sham group was 6%. The latter result is consistent with sham response rates referenced in IHS Guidelines for Migraine Trials. Sample size calculations are based on a more conservative estimate of the sham group response rate of 10%, then a sample size to detect a difference between treated and sham groups (of 20%) with 80% power at a 5% level of significance will result in a total of 124 evaluable subjects, with 62 subjects randomized to the treated arm and 62 to the sham arm. Allowing for a ~10% drop-out rate, a total of 136 (68 treated vs. 68 sham) subjects may be enrolled in the study.

Statistical considerations require availability of 124 evaluable subjects, i.e. with data available for analyses. The study recruitment will be monitored closely via the EDC system and, as soon as the evaluable data target is achieved, the Study Monitor will receive notification. If the number of subjects enrolled in the US is at least 50% of the accumulated population, recruitment will be stopped.

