7.6 Randomization

After a subject meets the eligibility criteria, he/she will be randomly allocated (with a 1:1 ratio) to one of the following 2 treatment groups based on a randomization scheme using the permuted block method stratified by preventive medications use and center:

- Sham Control
- Nerivio Migra group

The randomization scheme will be prepared by the study statistician using the SAS (version 9.4.) random number procedure. The block size will be fixed and study personnel will be blinded to the randomization block size.

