7.8 Statistical Analyses

Amendments to the statistical analyses section will not require IRB approval, unless driven by protocol or study design change. In that case a standalone SAP will be prepared prior to data lock for each analysis milestone.

7.8.1 *General Considerations*

Statistical analyses will be performed using SAS® v9.4 (SAS Institute, Cary NC, USA).

All statistical tests will be two-sided. The required significance level of findings will be equal to or lower than 5%, nominal p-values will be presented. Where confidence limits are appropriate, the confidence level will be 95%.

Continuous variables will be summarized by a mean, standard deviation, minimum, median and maximum, and categorical variables by a count and percentage. For comparison of means (continuous variables), the two-sample t-test or the Wilcoxon rank sum test will be used as appropriate. For comparison of proportions (categorical variables), the Chi-squared test or Fisher's exact test will be used as appropriate.

If multiple measurements are taken in a single patient, statistics described below will be appropriately modified to accommodate the within patient correlation.

7.8.2 *Significance levels and handling of type I error*

7.8.2.1 *Type I Error*

The overall significance level for this study is 5% using two-tailed tests, except for treatment by site interaction that will be tested at a significance level of 10%.

7.8.2.2 *Hierarchy Approach for Secondary Endpoints Analysis*

The hierarchy approach will be adopted for the primary and secondary endpoints to control type I error due to multiple endpoint testing. Thus, the primary endpoint will first be analyzed and only if $p < 0.05$, will the secondary endpoints be analyzed.

7.8.3 *Demographic and Other Baseline Characteristics*

Demographic and baseline condition related characteristics will be tabulated and compared between the study groups by data type. Continuous variables will be summarized by a mean, standard deviation, minimum, median and maximum, and categorical variables by a count and percentage.

This data will include:

- Demographic data
- Medical history
- Migraine preventive medication
- Other concomitant medication
- Migraine attacks characteristics per ICHD-3 diagnostic criteria for migraine with and without aura
- Physical examination
- Laboratory (pregnancy) tests for women of childbearing potential

7.8.4 *Disposition of Patients*

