The numbers of patients who entered the study and completed each stage of the study will be provided per month, as well as the reasons for all post randomization discontinuations, grouped by major reason, e.g., lost to follow-up, adverse event, poor compliance, did not administer any treatment (with reasons). A list of discontinued patients, protocol deviations, and patients excluded from the performance analysis will be provided as well.

7.8.5 *Performance Analyses*

Primary Performance Analyses:

The primary endpoint is freedom from pain at 2 hours post treatment without rescue medications in at least 50% of treated attacks, a count and percentage of subjects free from pain will be calculated and presented for both study groups each with a two-sided 95% exact confidence interval. The groups will be compared with a chi-squared test.

If the null hypothesis is rejected in favor of the alternative hypothesis and the proportion (%) of subjects reporting freedom from pain at 2 hours post treatment without rescue medications in the treated group is greater than that of the sham group, the study will be deemed successful.

The primary endpoint will also be evaluated stratified by center using a Mantel-Haenszel test to assess the center by group interaction.

A sensitivity analysis of the primary end-point will be performed to assess the impact of missing data on the study outcome. This will be performed using several possible imputation methods.

Subset analysis:

Adjustment for other covariates such as demographics or other baseline patient characteristics may be performed by adding these variables into a logistic regression model.

Subgroup analysis according to use of preventive medications will be performed and reported by adding these variables to a logistic regression model.

Secondary performance analyses:

The secondary performance variables will be summarized by a count and percentage and compared with a chi-squared test.

Exploratory performance analyses:

A count and percentage of patients reporting freedom from pain (pain grade 0) 48 hours post treatment without rescue medications in at least 50% of treated attacks will be presented, the groups will be compared with a chi-squared test.

Use of rescue medications will be summarized by descriptive statistics per treatment group and compared between the groups with a t-test.

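### The primary chi-squared test is valid and meets its planned power, but prespecified adjustment for preventive use and enrolment attack severity would be a low-cost improvement

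*Combined protocol and SAP*

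**What the plan says.** On the primary endpoint, Section 7.8.5 states: "The groups will be compared with a chi-squared test". Success is declared if that null hypothesis is rejected and the active group has the higher proportion. No stratum or covariate enters this test.

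Randomisation under Section 7.6 uses the "permuted block method stratified by preventive medications use and center" (Sections 6.1 and 6.2.1 name preventive use only). In the analysis these factors appear as follows:

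- **Preventive use:** a committed logistic-regression subgroup analysis, under the subset analyses of 7.8.5.
- **Center:** an additional Mantel-Haenszel analysis in 7.8.5 and a treatment-by-center interaction model in 7.9.
- **Other covariates:** optional and unnamed. "Adjustment for other covariates such as demographics or other baseline patient characteristics may be performed".

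Section 6.1 and the synopsis provide for recording "Baseline information including mean frequency and severity of migraine attacks". No analysis names that severity value.

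The plan does not describe the final test in one consistent way. Section 7.4 leaves open a regression model at the final analysis, 7.5 refers to the conventional test for the hypothesis, 7.8.1 allows chi-squared or Fisher's exact test, and 7.8.5 names chi-squared.

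**The concern.** A factor used to stratify randomisation is normally carried into the primary analysis, and a baseline variable expected to predict outcome can sharpen the comparison at no cost in patients. Here neither enters the analysis that decides success.

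Both candidates are plausible. The sponsor chose preventive use as a stratum. The pilot that supplied the planning rates required patients to be off preventive medication for at least two months (Section 4.2), so this trial adds a group with no pilot data. The endpoint is pain grade 0 whatever the starting grade, so patients with typically severe attacks may respond less often. That is inference: the documents report no association for either variable.

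At stake are a few points of power in a trial planned at 80%, and clarity about which model is primary. Enrolment mean severity is one value per subject, so it suits a per-subject endpoint without an attack-level model.

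**Working it through.** **Inputs from the documents.** 10% sham and 30% active response (7.4); 1:1 allocation; "with 80% power at a 5% level of significance will result in a total of 124 evaluable subjects"; and "All statistical tests will be two-sided" (7.8.1).

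**Step 1: reproduce the plan's figure.** Pooled-variance formula, no continuity correction, mean rate 0.20:

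n per arm = [1.960·√(2·0.20·0.80) + 0.842·√(0.30·0.70 + 0.10·0.90)]² / 0.20² = (1.109 + 0.461)² / 0.04 = 61.6, so 62 per arm and 124 in total.

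Power at 62 per arm = Φ[(0.20·√62 − 1.109) / 0.548] = Φ(0.851) = 80.3%.

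The unadjusted test delivers the planned power.

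**Step 2: responders available to a model.** 62·0.30 + 62·0.10 = 24.8 at the final analysis. At the interim look of 62 subjects, 31·0.30 + 31·0.10 = 12.4.

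**Step 3: approximate gain.** If the covariates explain a share R² of outcome variance (assumed), power ≈ Φ[(0.851 + 1.960)/√(1 − R²) − 1.960]. The N giving the same 80.3% power is 124·(1 − R²).

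| Assumed R² | Power at N = 124 | Equivalent N |
|---|---|---|
| 0 | 80.3% | 124 |
| 0.02 | 81.0% | 121.5 |
| 0.05 | 82.2% | 117.8 |
| 0.10 | 84.2% | 111.6 |
| 0.15 | 86.2% | 105.4 |

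**Step 4: simulation.** 3,000 trials per scenario, N = 124, permuted blocks within the preventive-use stratum, marginal rates fixed at 10% and 30%. Assumed: 35% preventive users, a standard-normal severity score, and the odds ratios (OR) shown. The Monte Carlo standard error of each power figure is √(0.8·0.2/3,000), about 0.7 points. Robust linear adjustment estimates a risk difference, adjusted for preventive use and severity.

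| OR, preventive use | OR per SD, severity | Chi-squared | Mantel-Haenszel by preventive use | Robust linear |
|---|---|---|---|---|
| 1 | 1 | 81.5% | 81.2% | 80.4% |
| 0.5 | 1 | 81.5% | 81.6% | 81.3% |
| 2 | 1 | 82.2% | 82.8% | 82.3% |
| 3 | 1 | 82.2% | 83.5% | 82.7% |
| 1 | 0.67 | 81.7% | 81.7% | 82.5% |
| 1 | 0.5 | 80.5% | 80.4% | 83.3% |
| 0.5 | 0.5 | 82.8% | 83.2% | 84.2% |
| 0.5 | 0.33 | 80.8% | 81.1% | 85.9% |

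The stratum alone changes power by about 0 to 1 point. With severity, the gain over chi-squared is 0.8 points at OR 0.67, 2.8 at OR 0.5 (1.4 when preventive use is also prognostic), and 5.1 in the strongest case. With no prognostic value, robust adjustment is 1.1 points lower, which is close to simulation error.

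**Step 5: type I error under 10% in both arms.** Chi-squared 4.8–5.2%; Mantel-Haenszel 4.8–5.2%; robust linear 4.4–5.1%; logistic likelihood-ratio test 5.7–6.4%. Separate simulations of an adjusted logistic score test gave 4.8–6.0%. The choice of method therefore matters at this sample size.

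**The case against.** The strongest reply is that nothing is wrong. The chi-squared test is valid and reaches 80.3% power, and every prognostic effect above is assumed. That stands, and it is why this is an improvement and not a defect.

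Part of an apparent gain can also be size inflation. A test with true size 5.8% would reach Φ(2.811 − 1.896), about 82.0%, with no real gain. When the adjusted score test and chi-squared were matched to 5% size (8,000 trials per setting, 20% null, preventive-use OR 0.55), the gain was about 0 points at severity OR 1.5, 2 at OR 2.0 and 4 at OR 2.5. This also stands, and it argues for a method that holds its level.

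Enrolment severity may be a weak covariate. Section 6.2 justifies the roll-in partly as a remedy for recall bias. In the pilot, mean attack pain was 8.9 in women and 8.6 in men on a 0–10 scale, against 4.6 at device activation, so the range may be narrow and distant from the pain treated. The enrolment scale is not stated, and the start-of-study questionnaire has no attack-severity item. These points favour the lower end of the range. They do not make roll-in severity preferable, because it is collected after randomisation, though before treatment.

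Three stronger readings are tempting but unsupported:

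- *The plan ignores preventive use.* It does not. Preventive use is a stratum and has a committed subgroup analysis.
- *Power is thrown away for nothing.* The documents show no prognostic association, so a loss cannot be demonstrated, and adjustment has small costs.
- *Optional covariates could change the success call.* Section 7.8.5 ties success to the primary null hypothesis and names one test for it. What remains open is the wording of 7.4 and 7.5.

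**Conclusion.** The point holds as a recommendation. The primary test leaves out a randomisation stratum and a baseline value the trial already records. Prespecifying both would probably help a little and would cost little power if they prove uninformative.

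The expected size is about 0 to 1 point from preventive use alone, about 1 to 5 points if enrolment severity is mildly to strongly prognostic (OR 0.67 to 0.33 per SD, the strongest case also assuming a preventive-use OR of 0.5), and about 0 if it is not. These figures rest on assumed odds ratios, an assumed 35% of preventive users and a normally distributed severity score. None of these can be checked in the documents.

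**What to change.** 1. In 7.8.5, name one primary analysis adjusted for preventive use and enrolment mean attack severity. Use a method that holds the 5% level with about 25 responders, such as a standardised or robust risk difference with 95% CI. At minimum, use a Mantel-Haenszel test stratified by preventive use.
2. Account for center as the other randomisation factor, or state how small centers are pooled, for example US versus non-US.
3. Use the severity value recorded at enrolment. Do not adjust for pain at the start of each treated attack, which arises after randomisation.
4. Keep the unadjusted chi-squared as a sensitivity analysis, and label any further covariate models exploratory.
5. Align 7.4, 7.5 and 7.8.1 with the named test. Compute interim conditional power on the same test, and confirm that the 36% and 80% zone limits still apply. Settle this before the unblinded look, where only about 12 responders are expected.

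The cost is plan wording, a stated severity scale, a rule for missing enrolment severity, and matching the interim calculation to the new test. No new patients are needed, and no new data if the enrolment form already captures severity on a usable scale.

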Participants will be instructed to activate the device at onset of a qualifying migraine attack and manually adjust stimulation intensity to a level within the pre-defined range where it is well perceived but not painful. A qualifying migraine attack shall be preceded by at least 48 hours of freedom from headache. Patients will be requested to refrain from use of rescue medications prior to and during the first two hours after treatment with the device, and if they can not comply with this, record their use of rescue medications (migraine specific drugs or other medications or therapies that may be used to treat pain, from a pre-specified list) in the mobile application.

Via the smartphone application, each participant will be asked to rate his/her migraine pain level three times using Pain Grades Scale (0 - no pain, 1- mild pain, 2- moderate pain, 3 – severe pain): (1) upon starting the treatment, (2) two hours after start of treatment, (3) 48 hours after start of attack. At the start of each treatment, participants will be also asked to provide time elapsed from start of migraine attack to start of the treatment. Participants will be also asked to provide feedback regarding their use of medication (migraine specific drugs or other medications or therapies that may be used to treat pain, from a pre-specified list), presence of nausea, photophobia and phonophobia, and treatment perception. After providing feedback at two hours

after start of treatment and in case of pain recurrence, participants will be allowed to re-treat the attack using Migra device.

Adverse events will be reported.

Duration of study participation for each patient will be up to three months, determined by one month of the roll-in stage followed treatment of four qualifying attacks over the course of two months (whichever is achieved first).

Post study questionnaire will include patient global impression of change [27], blinding and usability assessments.

Stage Three. This part will include open label extended treatment. Following the completion of the study by all subjects and the return of all study devices, subjects will be offered a 2-month period of using active device, at no cost.

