6.3.2 Secondary Endpoints

Secondary Performance Endpoints

1. The proportion (%) of subjects reporting treatment response at 2 hours post treatment without rescue medications in at least 50% of treated attacks. Treatment response is defined as: pain level reduction from moderate or severe at baseline to mild or pain level of none if treatment started with mild pain
2. Proportion (%) of patients reporting, 2 hours post treatment:
 - freedom from pain (pain grade 0) and their most bothersome migraine-associated symptom (MBS) in at least 50% of treated attacks
 - freedom from nausea in at least 50% of treated attacks
 - freedom from photophobia in at least 50% of treated attacks
 - freedom from phonophobia in at least 50% of treated attacks

6.3.3 Exploratory Endpoints:

1. The proportion (%) of patients reporting freedom from pain (pain grade 0) 48 hours post treatment without medications in at least 50% of treated attacks

2. The percent of subjects who are pain-free at 2 hours with no use of rescue medication, and either have no relapse of pain within the subsequent 46 hours, or, if they have a relapse of pain in this time window, it disappears every time, after two hours, using the device, with no use of rescue medications.
3. Patient global impression of change, with emphasis on disability and quality of life.

6.3.4 Safety Endpoints:

- Treatment tolerability
- Adverse events and complications whether related or unrelated to study device.

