7 STATISTICAL CONSIDERATIONS

7.1 *Study Design and Aim*

The study is designed as a prospective, randomized, double-blind, sham controlled multi-center clinical trial. The study aim is to demonstrate safety and effectiveness of Nerivio Migra electro stimulation device for treatment of migraine attacks with and without aura.

7.2 *Study Variables*

7.2.1 *Primary performance variable*

The primary performance endpoint, the proportion (%) of patients reporting freedom from pain (pain grade 0) 2 hours post treatment without rescue medications in at least 50% of treated attacks, will be measured in the form of a binary variable which will be assigned the value of "1" if the subject reports freedom from pain (pain grade 0) 2 hours post treatment without rescue medications in at least 50% of his/her treated attacks, and "0" otherwise.

7.2.2 *Secondary performance variables*

The secondary performance endpoints will all be expressed in the form of binary variables as in the representation of the primary performance variable.

7.2.3 *Exploratory performance variables*

The exploratory performance endpoint, the proportion (%) of patients reporting freedom from pain (pain grade 0) 48 hours post treatment without rescue medications in at least 50% of treated attacks, will be measured in the form of a binary variable which will be assigned the value of "1"

if the subject reports freedom from pain (pain grade 0) 48 hours post treatment without rescue medications in at least 50% of his/her treated attacks, and “0” otherwise.

Patient global impression of change is measured via a questionnaire.

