Patient global impression of change will be summarized by descriptive statistics per treatment group and compared between the groups with a t-test.

Ease of use will be summarized by descriptive statistics.

7.8.6 *Safety Analysis:*

The primary safety variable, the cumulative incidence (and 95% CI) of device related adverse events (AEs) throughout the study, will be presented in tabular format and will include incidence tables by severity.

Adverse event rates will be compared between the study groups with a chi-squared test.

Serious adverse events will be listed and discussed individually.

Treatment tolerability will be compared between the study groups, the number and percent of subjects who fail to complete the study and the number and percent of subjects who fail to complete the study because of Adverse Events will be presented as well.

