APPENDIX B- SUBJECT QUESTIONNAIRES

Appendix B. Subjects' questionnaires **NM1 MCT – Start of Study Questionnaire**

The Migraine Disability Assessment questionnaire was put together to help you measure the impact that migraines (and headaches) on your life.

Please answer all the following questions regarding ALL the migraines you've had in the past 2 months. For each question, select one choice.

Part I – Migraine Disability Assessment

Establishing baseline

1. How many days per month, in the 2 months before the study, did you miss work or school because of your migraine?
 1. 0
 2. 1-3
 3. 4-8
 4. More than 8
2. In how many days per month, in the 2 months before the study, was your productivity at work or school significantly reduced because of your migraine (do not include days that you indicated in question #1)?
 1. 0
 2. 1-3
 3. 4-8
 4. More than 8
3. In how many days per month, in the 2 months before the study, did you not do household work because of your migraine (such as housework, home repairs or maintenance, shopping, caring for children, etc.)?
 1. 0
 2. 1-3
 3. 4-8
 4. More than 8
4. In how many days per month, in the 2 months before the study, was your productivity in household work significantly reduced because of your migraine (such as housework, home repairs or maintenance, shopping, caring for children, etc.)?
 1. 0
 2. 1-3
 3. 4-8
 4. More than 8
5. On how many days per month, in the 2 months before the study, did you miss family, social or leisure activities because of your migraine?
 1. 0
 2. 1-3
 3. 4-8
 4. More than 8
6. In general, how would you grade the degradation in your quality of life as a result of migraines?
 1. None
 2. Mild effect
 3. Moderate effect

4. Severe effect
7. How much do you typically spend on migraine medication, per month?
 1. Less than \$10
 2. \$11-\$20
 3. \$21-\$50
 4. More than \$50

NM1 MCT – End of Study Questionnaire

The Migraine Disability Assessment questionnaire was put together to help you measure the impact that migraines (and headaches) on your life.

Please answer all the following questions regarding ALL the headaches you've had in the past 2 months. For each question, select one choice.

1. How many days per month, in the last 2 months, did you miss work or school because of your migraine?
 1. 0
 2. 1-3
 3. 4-8
 4. More than 8

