2. In how many days per month, in the last 2 months, was your productivity at work or school significantly reduced because of your migraine (do not include days that you indicated in question #1)?
 1. 0
 2. 1-3
 3. 4-8
 4. More than 8
3. In how many days per month, in the last 2 months, did you not do household work because of your migraine (such as housework, home repairs or maintenance, shopping, caring for children, etc.)?
 1. 0
 2. 1-3
 3. 4-8
 4. More than 8
4. In how many days per month, in the last 2 months, was your productivity in household work significantly reduced because of your migraine (such as housework, home repairs or maintenance, shopping, caring for children, etc.)?
 1. 0
 2. 1-3
 3. 4-8
 4. More than 8

5. On how many days per month, in the last 2 months, did you miss family, social or leisure activities because of your migraine?
 1. 0
 2. 1-3
 3. 4-8
 4. More than 8
6. In the past two months, how would you grade the degradation in your quality of life as a result of migraines?
 1. None
 2. Mild effect
 3. Moderate effect
 4. Severe effect
7. How much do you typically spend on migraine medication, per month, during the 3-months study?
 1. Less than \$10
 2. \$11-\$20
 3. \$21-\$50
 4. More than \$50

Part II – Device Usability and Pricing

1. If you could purchase the device now, how much would you be willing to pay for it, per month?
 1. Less than \$10
 2. \$11-\$20
 3. \$21-\$50
 4. More than \$50
2. If you had the device permanently in your possession, what would be your estimate for additional (extra) spending on medication?
 1. Less than \$10
 2. \$11-\$20
 3. \$21-\$50
 4. More than \$50
3. If you had the device permanently in your possession, what would be your estimate for additional (extra) spending on medication?
 1. Less than \$10
 2. \$11-\$20
 3. \$21-\$50
 4. More than \$50

4. How likely are you to recommend using NM1 device for a friend or family member that also suffer from migraines?
 1. Not likely
 2. Likely
 3. Very likely
 4. Extremely likely
5. How likely would you be willing to share the information about your migraine episodes with your physician or any other designated care-taker, via the device and its App?
 1. Not likely
 2. Likely
 3. Very likely
 4. Extremely likely

Did you experience any inconvenience during the treatment?

6. Itching at the location of the device?
 1. None
 2. Mild
 3. Moderate
 4. Severe
7. Skin redness at the location of the device?
 5. None
 6. Mild
 7. Moderate
 8. Severe

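### The disability and quality-of-life exploratory endpoint has only a two-group t-test stated for it; adjusting for the start-of-study answers already collected would add precision at almost no cost

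*Combined protocol and SAP*

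**What the plan says.** Section 6.3.3, item 3, defines the endpoint as "Patient global impression of change, with emphasis on disability and quality of life". Section 7.2.3 adds only that "Patient global impression of change is measured via a questionnaire", without naming items, a score or a derivation. Section 6.1 places it at the end of the trial: "Post study questionnaire will include patient global impression of change [27], blinding and usability assessments". The analysis, in the exploratory part of section 7.8.5, is "Patient global impression of change will be summarized by descriptive statistics per treatment group and compared between the groups with a t-test".

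Appendix B prints a Start of Study Questionnaire, whose first part is headed "Establishing baseline", and an End of Study Questionnaire. Items 1 to 5 (lost or reduced days at work, in the household and in social life) and item 6 (quality of life) appear on both forms, each with the same four ordered answers.

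Three other places in section 7 could have brought in the start-of-study answers:

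- Section 7.8.3 lists the baseline data to be tabulated. The questionnaire is not on the list.
- The subset-analysis paragraph of 7.8.5 allows covariate adjustment, but as an option and by logistic regression, which does not suit a score compared by t-test.
- Section 7.8.1 has a general rule: "If multiple measurements are taken in a single patient, statistics described below will be appropriately modified to accommodate the within patient correlation". It names no model, outcome or covariate.

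**The concern.** The trial asks patients about disability and quality of life before treatment and again at the end, and an exploratory endpoint emphasises exactly that domain. If the endpoint is built from those items, patients who start with heavy disability are likely to end with more of it too. An analysis of end values alone leaves those stable differences in the error term. A change score removes them only imperfectly. Either way the confidence interval for the arm difference is wider than the collected data allow, and a real effect on disability or quality of life is easier to miss. Because the score is undefined, the choice between end value, change and adjusted analysis would also remain open when the data are in hand.

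**Working it through.** **The plan's own figure.** Section 7.4 gives 30% against 10% responders, two-sided 5%, 80% power and a chi-squared test. Per arm, n = [1.96·√(2·0.20·0.80) + 0.842·√(0.30·0.70 + 0.10·0.90)]² / 0.20² = (1.109 + 0.461)² / 0.04 ≈ 61.6, so 62 per arm and 124 in total, as stated. The plan gives no figure for the exploratory endpoint, so 62 per arm is used below.

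**Variance of the arm difference.** Let r be the within-arm correlation between start and end scores, with equal variances at both times. Take the end-value t-test as 1.

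- Change-score t-test: 2(1 − r)
- ANCOVA on the start score: 1 − r²
- ANCOVA relative to change score: (1 − r²) / [2(1 − r)] = (1 + r)/2, which is below 1 for every r below 1

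| r (assumed) | End value | Change score | ANCOVA | ANCOVA ÷ change |
|---|---|---|---|---|
| 0.3 | 1 | 1.40 | 0.91 | 0.65 |
| 0.5 | 1 | 1.00 | 0.75 | 0.75 |
| 0.7 | 1 | 0.60 | 0.51 | 0.85 |

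Below r = 0.5 a change-score t-test is worse than ignoring the baseline.

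**Detectable difference at 80% power, 62 per arm.** End value: (1.96 + 0.842)·√(2/62) = 0.503 SD. Multiplying by the square root of each variance ratio gives:

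| r | Change score | ANCOVA | ANCOVA power at 0.503 SD | Total N giving ANCOVA 80% (124 × (1 − r²)) |
|---|---|---|---|---|
| 0.3 | 0.595 SD | 0.480 SD | 83.6% | about 113 |
| 0.5 | 0.503 SD | 0.436 SD | 89.9% | about 93 |
| 0.7 | 0.390 SD | 0.359 SD | 97.5% | about 63 |

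**Check on one four-category item.** The formulas are for continuous scores, so a single item was simulated: 62 per arm, latent normal scores cut into four roughly equal categories, latent shift 0.55, 4,000 trials per setting. Power for end-value t, change-score t and ANCOVA was 80/62/81% at an observed r of 0.26, 80/73/87% at 0.44 and 79/88/94% at 0.63. With no shift, all three rejected in 4.3% to 5.4% of trials.

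**If the endpoint is one end-of-study global rating.** It then has no baseline value of its own. Using the start-of-study score as covariate cuts variance by r²: 1%, 4% and 9% at r = 0.1, 0.2 and 0.3.

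**Is the start form usable as a covariate?** Section 6.6.2 puts a questionnaire at the screening and enrolment visit, while the synopsis places a quality-of-life questionnaire in the roll-in stage. Both come before Stage Two treatment, and the day-count items ask about the two months before the study.

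**The case against.** The strongest reply is that the quoted sentence concerns a global impression of change. Such a rating is normally given once, after treatment, with change built into the question, so a comparison without a baseline is ordinary. No text says that Appendix B items 1 to 6 are that rating; the forms introduce them as a migraine disability assessment. Appendix B as supplied shows neither a global-change item nor the blinding item promised in section 6.1, so the relevant item may simply not be visible. This stands, and the fix therefore leaves any separate global-change item alone. The disability and quality-of-life items collected twice would then have no stated analysis.

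A reader might infer that the plan throws the baseline away altogether. The documents do not support that. The score is undefined, and an endpoint named as change could be the start-to-end difference, which does use the start answers. The general rule in 7.8.1 could also be read to cover it, although it specifies nothing. What can be said is that no stated analysis uses these answers.

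A reader might also take the two forms to be identical. They are not. The introduction refers to migraines at the start and headaches at the end. The quality-of-life item asks "In general, how would you grade the degradation in your quality of life as a result of migraines" at the start but "In the past two months, how would you grade the degradation in your quality of life as a result of migraines" at the end. Such differences could lower the correlation on which the gain depends.

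Finally, chance imbalance at 62 per arm is not a bias. It is already reflected in the test's 5% error rate.

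**Conclusion.** The point holds as a free improvement in precision, not as a flaw in validity. If the endpoint is a score built from Appendix B items 1 to 6, ANCOVA is at least as precise in large samples as either t-test that the plan could mean. The saving against an end-value t-test is material when r is about 0.5 or more and small at 0.3 or less. Against a change-score t-test the order reverses: the saving is largest when r is low. The size rests on an assumed r, on equal start and end variances, and on 62 per arm; the variance ratios themselves do not depend on the sample size. If the endpoint is a single global rating, the stated comparison is reasonable and adjustment would add little. Priority is low, because the endpoint is exploratory, lies outside the primary and secondary hierarchy of 7.8.2.2, and has no power target or decision rule.

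**What to change.** In section 7.8.5:

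1. State which item or score is the endpoint.
2. For the Appendix B disability and quality-of-life items, analyse the end-of-study sum of items 1 to 6 by ANCOVA, with arm, the start-of-study sum and the preventive-medication stratum as terms. Report the adjusted difference with a 95% CI.
3. Add proportional-odds models for the single items, each adjusted for its own start-of-study answer and the same stratum, as supportive analyses.
4. If a separate single global-change item is asked at the end of the study, keep its between-group comparison as now stated.

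The cost is a few sentences of analysis wording, including the definition of the sum score. No new data, patients or visits are needed. Section 7.8 says that changes to the statistical section need no IRB approval unless driven by a protocol or design change, and section 9 treats the SAP as a separately modified document. The wording should be settled before unblinding, so that the choice of score is not made with the results in view.
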